## 1. STUDY OBJECTIVES

Our overall aim is to conduct a 1-year double blind randomized control trial comparing candesartan to lisinopril in 140 individuals with hypertension and executive mild cognitive impairment. Our specific aims are:

**Aim 1:** Investigate the effect of candesartan compared to lisinopril on the progression of cognitive function evaluated by a battery of neuropsychological tests assessing executive function, memory, attention and cognitive speed in hypertensive older adults with executive mild cognitive impairment.

**Hypothesis 1:** Candesartan is associated with less decline in executive function compared to lisinopril.

**Aim 2:** Investigate the effect of candesartan compared to lisinopril on cerebral perfusion, cerebrovascular reserve (vasoreactivity to carbon dioxide) assessed by arterial spin labeling MRI and microvascular brain injury reflected by diffusion tensor imaging measures of connectivity.

**Hypothesis 2:** Candesartan is associated with less decline in cerebral perfusion, vasoreactivity to carbon dioxide, and evidence of microvascular brain injury (white matter integrity) compared to lisinopril.

**Aim 3:** Identify underlying mechanisms explaining the effects of candesartan on neuroimaging (AIM 3A) and cognitive (AIM 3B) outcomes relative to lisinopril including effects on arterial stiffness, atherosclerosis (carotid intima-media thickness, CIMT), and vascular inflammatory and endothelial markers.

**Hypotheses 3:** Relative to lisinopril, treatment with candesartan is associated with lower CIMT, arterial stiffness, and inflammatory and endothelial function markers at 12 months, which in turn are associated with improved cerebral perfusion, vasoreactivity, and white matter integrity measures (Hypotheses 3A) as well as less decline in executive function (Hypotheses 3B) at 12 months.

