*5. Mechanistic approach for the effect of ARBs on the brain:* To further support our AT2 hypothesis in the brain, we will measure processes that are likely to be affected by AT2. AT2 activation is associated with decreases in vascular remodeling and inflammation and restores endothelial dysfunction by improving NO homeostasis. Increased vascular stiffness and atherosclerosis reflected by higher carotid intima-media thickness (CIMT) contributes to vascular brain injury and cognitive impairment. AT1 activation leads to greater atherosclerosis and vascular stiffness and ARBs, more so than ACEIs, lower CIMT and arterial stiffness. In the cerebral arteries, candesartan resulted in the normalization of mean media thickness, leading to decreased arterial stiffness. ARBs also lower inflammatory markers, more so than ACEI, and restore proper endothelial function possibly via AT2 hyperstimulation. Inflammation also impairs endothelial function and increases atherosclerosis. Recent evidence suggests that proper endothelial function requires the replacement of dysfunctional cells and that endothelial progenitor cells (EPC) function as a reservoir for newer endothelial cells. The number of EPC has been linked with arterial stiffness, atherosclerosis, vascular brain injury and dementia. ARBs may improve the proliferation and function of EPCs in hypertension via an antioxidant effect. Therefore the potential mechanisms by which ARBs may prove to be superior to ACEIs in the brain may be related to their effects on atherosclerosis, vascular stiffness, inflammation, and optimal endothelial function and turnover. This project will test these hypotheses.

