(ii) Inflammation, endothelial function markers, and APOE: We selected inflammatory biomarkers based on the evidence that the marker may be associated with cognition and/or is affected by RAS/ARB. Various studies have suggested that these inflammatory markers are associated with cognitive function, increased in hypertension, and modulated by Ang II: C-reactive protein (CRP), cytokines (TNF- $\alpha$ , interleukin family), vascular adhesion molecules (ICAM, VCAM, E- and P-selectin), metalloprotease 9 (MMP9) fibrinogen, von Willebrand factor (vWF) and plasminogen activator inhibitor-1 activity (PAI-1). Endothelial progenitor cells (EPC) will be measured according to methods previously described. Mononuclear cells will be first isolated by density gradient from 10 cc of blood. EPC will be identified by the expression of surface antigens CD34+KDR+ which provides the best balance between cell count and accuracy (ICC=0.81, CV<10%), and reported as the number of cells per cytometric event to avoid error inflation due to variation in total blood cells. We will use EPC and adhesion molecules to further investigate the association between cerebrovascular reactivity and endothelial function. EPC measurement will be completed at ECCRI ([name]) at Emory and inflammatory markers and urinary proteins (including isoprostanes) will be done at the University of Southern California or the Foundation for Health Improvement and Technology (FHIT). Blood/urine samples will be stored at ACTSI then mailed to USC or FHIT in batches. We will perform baseline, 12 months assessments of the inflammatory biomarkers and baseline, 6 and 12 months assessments of the EPC

and urine chemistries. Blood samples will be drawn at baseline for APOE genotype as well. APOE will be performed USC or FHIT.

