(b) Role of vascular/inflammatory measures: Mediation analysis with bootstrapping will be used to identify the potential role of the vascular, endothelial and inflammatory markers on both our cognitive outcomes and neuroimaging outcomes. This method is particularly useful in clinical trials since it has superior statistical power for relatively small sample sizes. It also does not require a large effect size of the intervention on the outcome. The independent variable is treatment assignment. The dependent measures are executive function (EXAMINER score) and neuroimaging variables [perfusion, VR, VMR, FA, MD]. The potential mediators are [CIMT, stiffness (DIS, COMP), endothelial and measures (EPC, CRP, cytokines, VCAM, ICAM, MMP and PAI1)]. For each mediator, an estimation of the mediation effect will be calculated using the Freedman-Schatzkin difference in the regression coefficients ( $\beta_1 - \beta_2$ ) for the treatment effect obtained from the 2 regression models with and without the mediator: (outcome =  $\alpha + \beta_1 \times \text{treatment}$  and outcome =  $\alpha + \beta_2 \times \text{treatment} + \gamma \times \text{mediator}$ ). Bootstrapping method (5000 random samples) will be used to obtain the empiric distribution of the mediation effect and a mean, standard error and a confidence interval will be calculated. The null hypothesis for mediation is that the difference-in-coefficients ( $\beta_1 - \beta_2$ ) is zero.

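### Section 10.5(b) tests at least 60 mediator–outcome pairs one at a time, with no multiplicity rule, lead mediator or exploratory label, although Aim 3 is framed as directional hypotheses

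*Combined protocol and SAP*

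**What the plan says.** Section 10.5, Outcome Analysis part (b), sets out the mediation analysis for Aim 3.

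- **Mediators:** "The potential mediators are [CIMT, stiffness (DIS, COMP), endothelial and measures (EPC, CRP, cytokines, VCAM, ICAM, MMP and PAI1". That is ten entries, with cytokines counted once. Section 6.5 shows that cytokines cover TNF-α and the "interleukin family".
- **Outcomes:** "The dependent measures are executive function (EXAMINER score) and neuroimaging variables [perfusion, VR, VMR, FA, MD". That is six.
- **Method:** "For each mediator, an estimation of the mediation effect will be calculated using the Freedman-Schatzkin difference in the regression coefficients", taken from the treatment coefficients with and without the mediator in the model. Then: "Bootstrapping method (5000 random samples) will be used to obtain the empiric distribution of the mediation effect", summarised by its mean, standard error and an interval whose type and level are not given.
- **Test:** "The null hypothesis for mediation is that the difference-in-coefficients" is zero.

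Section 1 gives Hypotheses 3 a direction: "treatment with candesartan is associated with lower CIMT, arterial stiffness, and inflammatory and endothelial function markers at 12 months, which in turn are associated with" better imaging measures (3A) and less executive decline (3B). Section 10.1 repeats them as hypotheses. Item 5 of Section 2.1 ends its account of the candidate mechanisms with "This project will test these hypotheses".

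Table 3 puts the markers in a row of their own, with no ranking. The only control of the error rate over several tests is the O'Brien-Fleming rule in Section 10.3, for interim looks at EXAMINER.

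**The concern.** Aim 3 is meant to say why candesartan differs from lisinopril. Sixty or more unadjusted tests, none designated as the main one, leave room for a chance result to be presented as the mechanism even if candesartan alters no marker.

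The false results would also tend to arrive together. All six tests on one marker use the same estimated treatment effect on that marker, so a single chance imbalance can make several outcomes appear to agree, which looks like replication. A reader of the results could not tell how many pairs had been examined.

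**Working it through.** The documents give no error rate for Aim 3, so there is no stated figure to reproduce.

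**1. Count.** 10 mediators × 6 outcomes = 60 pairs. This is a minimum, because cytokines are more than one assay.

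**2. What each test estimates.** In linear models, β1 − β2 = a × γ. Here a is the treatment effect on the marker and γ is the slope of outcome on marker, adjusted for treatment. The six tests on one marker share a.

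**3. Reference bounds.**
- Sixty independent 5% tests: 1 − 0.95^60 = 95.4%.
- Ten independent 5% tests: 1 − 0.95^10 = 40.1%.

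Because a is shared within each marker, the second figure is close to the practical ceiling and the first is not relevant.

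**4. Simulation of the written procedure.**
- From the documents: 140 analysed, 70 per arm; one mediator and one outcome per model; difference in coefficients with a bootstrap.
- Assumed: no treatment effect on any marker or outcome, multivariate normal data, 95% percentile intervals, and the correlations shown.
- 1,500 trials × 2,000 resamples (the plan uses 5,000), Monte Carlo SE about 1.2 points.

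| Marker–marker r | Outcome–outcome r | Marker–outcome r | Any of 60 false | Any of 10 EXAMINER tests false | Mean false pairs when any |
|---|---|---|---|---|---|
| 0.3 | 0.3 | 0 | 7.7% | 2.0% | 1.3 |
| 0.3 | 0.3 | 0.1 | 20.0% | 6.5% | 2.2 |
| 0.5 | 0.5 | 0.1 | 14.9% | 6.3% | 3.3 |
| 0.15 | 0.5 | 0.2 | 35.7% | 24.1% | 5.0 |
| 0.3 | 0.3 | 0.2 | 36.0% | 23.6% | 5.0 |
| 0.5 | 0.5 | 0.2 | 27.7% | 19.1% | 6.2 |
| 0.7 | 0.7 | 0.2 | 18.0% | 12.3% | 8.8 |
| 0.3 | 0.3 | 0.3 | 36.6% | 33.3% | 7.4 |
| 0.5 | 0.5 | 0.3 | 31.0% | 28.4% | 9.6 |
| 0.7 | 0.5 | 0.3 | 20.9% | 19.3% | 12.6 |
| 0.5 | 0.5 | 0.4 | 30.2% | 30.0% | 10.2 |

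Some participants will have no MRI. With 100 analysed instead of 140 (an assumption), the (0.5, 0.5, 0.3) case gives 30.3% in place of 31.0%. Smaller runs with fewer trials and resamples reached 41–42% at the top, and about 10% with unrelated markers.

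**5. Interval type.** The text also allows mean ± 1.96 × bootstrap SE. With outcome–outcome r = 0.5 (700 trials × 1,000 resamples), the rates by (marker–marker, marker–outcome) r were:
- (0.2, 0.1): 3%
- (0.2, 0.2): 14%
- (0.2, 0.3): 28%
- (0.5, 0.2): 11%
- (0.5, 0.3): 21%

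Percentile intervals in the same runs gave 22–42%.

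**6. Direction.** Counting only false findings that favour candesartan, the percentile rates in those runs were 11–22%, and 4–20% for EXAMINER alone.

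**7. Effect of adjustment** (percentile intervals, correlated scenarios in the table plus the 100-participant case). Bonferroni over the ten mediators (99.5% intervals) gives 1.0–6.0%. Bonferroni over all sixty pairs (99.92%) gives 0.3–2.1%, though these extreme quantiles are imprecise with 2,000 resamples.

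**The case against.** The plan has some hierarchy. Table 3 names one primary outcome and keeps mediators separate, Section 10.1 puts the marker hypotheses in a second set, and Section 10.5(b) speaks of potential mediators. The primary test has its own alpha control. Hypotheses 3 are directional, so about half of the false intervals would contradict them. The size also depends on correlations and an interval type that the documents do not state.

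The points on size and direction stand and are built into the ranges given. The points on hierarchy do not settle the matter. Calling a mediator potential is not an exploratory label when the same paragraph states a null hypothesis for the mediation effect, and a wrong-direction interval could still be reported. Nor is zero marker–outcome correlation the protocol's own picture: Section 2.1 says that stiffness and CIMT contribute to brain injury and cognitive impairment, and Section 6.5 chose inflammatory markers partly for a link with cognition.

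Four stronger readings are tempting, and the documents support none of them.
- **A false mechanism is almost certain (95.4%).** That treats 60 tests as independent, but they share treatment-on-marker estimates.
- **A rate such as 20–37% is a property of the plan.** It holds only under assumed correlations and percentile intervals.
- **The plan will report any interval that excludes zero as the mechanism.** No section sets such a rule; the plan simply does not prevent it.
- **The Background sentence commits the trial to confirmatory tests of 3A and 3B.** That sentence closes a discussion of mechanisms and mentions neither. The directional framing comes from Sections 1 and 10.1.

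**Conclusion.** The concern holds for Aim 3. At least 60 pairs are tested singly, with nothing to limit what may be claimed from them.

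If candesartan changes no marker and markers correlate about 0.1–0.4 with outcomes, the chance of at least one false mediation finding is roughly 15–40% with 95% percentile intervals, about half of it in the hypothesised direction. It is roughly 3–28% with mean ± 1.96 SE intervals. With percentile intervals and markers unrelated to outcomes it is about 7–10%. At marker–outcome correlations of 0.2–0.3, a trial with any false finding shows on average about 5 to 13 false pairs.

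The correlations, the 95% level, the interval type and normality are assumptions; the sample size, the count of pairs and the method come from the documents. The primary EXAMINER treatment comparison is not affected.

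**What to change.** In Section 10.5(b):

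1. Declare the mediation analyses for Hypotheses 3A and 3B exploratory.
2. Replace the null-hypothesis sentence with estimation: the mediation effect and its bootstrap interval, with interval type and level stated.
3. Report all pairs and the number examined.
4. State that no mechanism will be claimed as identified from a single interval that excludes zero.

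If the sponsor wants a confirmatory mediation claim, it should instead name the mediator–outcome pairs before unblinding and adjust the bootstrap intervals for their number. As an illustration, four named mediators on EXAMINER alone with 98.75% intervals (0.05/4 = 0.0125) gave a false-claim rate of 0.4–5.4% in simulation, but that choice would leave 3A without a confirmatory test. A Bonferroni adjustment over all 60 pairs would need more than 5,000 resamples, because 5,000 × 0.05/60/2 leaves only about 2 in each tail.

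The change is to wording only, with no new data or visits. The cost is that Aim 3, including 3A, yields no confirmatory mechanism claim or, under the alternative, that each pre-specified pair has lower power.

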**7.2.3 Enrollment, Baseline, and Randomization:** During this phase, blood pressure measurements, detailed neuropsychological assessments, physical exam, brain MRI, and carotid ultrasound will be completed. Blood samples will also be collected for APOE, inflammatory and endothelial markers. Randomization and study intervention will occur after baseline data collection. Participants will then be started on the study medications. For all study related testing, the test results will not be disclosed to you unless deemed necessary by the study Physician.

**7.2.4 Follow-up Visits:** Following randomization, participants will be seen every two weeks, where antihypertensive study medications will be increased until they achieve blood pressure control (<140/90 mmHg), according to the designated trial protocol for blood pressure control. Blood pressure, heart rate, weight, adverse events (AE) and serious adverse events (SAE), pill count (to assess compliance), and use of non-study medications data will be collected. Once hypertension control is achieved, participants will be seen at 3, 6 and 12 months visits. Repeat neuropsychological assessment, blood draws (EPC and inflammatory markers), and urine collection will be conducted at the 6 and 12 months visit. Repeat neuroimaging and vascular ultrasound will be repeated at 12 months. BMP will also be checked at 2 weeks after randomization if only step one is needed, 4 weeks post randomization if treatment beyond step 1 is needed, and at 3, 6 and 12 months as shown in **Table 2**. Participants will also be contacted by phone as described in Table 2, Monthly during the follow-up phase. During these phone calls, participants will be asked about missing any doses in their medications and screened for any potential adverse events.

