#### 10.4 Outcomes

Table 3 provides a list of main outcomes. Other Analyses' variables: Logical memory, digit span, DSST, WMH volume, regional brain measures

**Table 3:** Independent, primary and secondary outcomes and other variables to be used in the analyses

Independent:	Randomization Group (Candesartan vs Lisinopril)
Primary outcome:	Executive function (EXAMINER score)
Secondary Imaging outcomes:	Perfusion, CO2 VR, VMR, FA, MD, DTT t-scores, rs-fMRI
Mediators:	CIMT, stiffness, inflammatory markers, EPC
Tertiary outcomes:	memory, digit span, DSST, WMH volume, regional brain measures
Stratification variable:	Race, number of antihypertensive medications
Covariates:	Prior stroke and prior use of ACEI/ARB
Safety:	AE, SAE, incident dementia

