#### Outcome Analysis

(a) Candesartan and cognitive/neuroimaging outcomes: General linear models will be used to compare the candesartan and lisinopril groups. Our main explanatory variable is the indicator for treatment group. Dependent variables will be the 12-month cognitive and neuroimaging measurements. For the cognitive analyses, our primary outcome is the executive function score derived using item response theory as outlined above in the EXAMINER methodology to account for education, age, and race influences on measures of executive abilities (developed by our collaborator, [name] team). For the cognitive outcome Mixed models with repeated measures (3 measurements) will be used. This procedure allows us to model the covariance structure to account for the potential variability across subjects in times of follow-up visits. Our main explanatory variable is the indicator for treatment group. The test of treatment effects on trial outcomes will be an interaction of treatment by visit (baseline,12 months follow-up). The main covariate adjustments will include history of prior stroke and prior exposure to ACEI/ARB. Additional covariate adjustments will be selected based on baseline statistically significant differences between the 2 randomized groups. The neuroimaging outcomes include measures of global perfusion, reactivity, FA, MD, and tractography metrics described above. **Table 3** provides a list of main variables. The multivariate models of the neuroimaging analysis will include the baseline values of the 12-month outcome variable, randomization stratification variables and other covariates that are significantly differ (at p<0.05) between the 2 groups at baseline. We will assess if the effects of randomized treatment are independent of blood pressure by comparing models with and without blood pressure change from baseline to 12 months. Summary statistics will include the model-adjusted mean and 95% confidence interval for each treatment group, and the mean (95% confidence interval) group difference on each 12-month outcome, as well as a p-value for group differences. All tests of significance on treatment group comparisons will use a two-sided alpha of 0.05.

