## 10.6 Sample Size Estimates

Using ANOVA with repeated correlated measures improves power in clinical trials. The 1 year correlation with baseline repeated measures ranged from 0.3 to 0.5 in our pilot data. The effect size for candesartan relative to lisinopril was 0.48 [mean difference 12 (pooled SD 25 sec)] for TMT-B, 0.41 [mean 5.5(13)] for cerebral blood flow and 0.24 [mean 0.30(1.2)] for vasoreactivity to CO2 in our pilot study. Using a 2-sided  $\alpha = 0.05$ , we estimate that a sample size of 140 will give us 80% power to detect at least 0.24 effect size. To account for dropout rate of 10-15% and a 55% prevalence of eligible subjects, we estimate that we need to screen 332 and enroll 160 to achieve a 140 final sample size.

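### Aim 3 mediation models omit baseline marker and outcome values, so if candesartan shifts a marker, pre-existing marker-brain correlation can be reported as mediation

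*Combined protocol and SAP*

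**What the plan says.** Part (b) of the Outcome Analysis in section 10.5 gives two regressions for each mediator: outcome = α + β1 × treatment, and outcome = α + β2 × treatment + γ × mediator. The mediation effect is β1 − β2, the difference in coefficients "for the treatment effect obtained from the 2 regression models with and without the mediator". It is bootstrapped with 5000 samples and tested against zero.

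Baseline terms appear elsewhere. In part (a), the neuroimaging models "will include the baseline values of the 12-month outcome variable, randomization stratification variables". Table 3 in section 10.4 lists the stratification variables and, as covariates, "Prior stroke and prior use of ACEI/ARB". Nothing carries these terms into the part (b) equations, and the baseline mediator is not added anywhere.

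Part (b) does not say whether 12-month values or changes are analysed. Hypotheses 3 in section 1 point to levels: "treatment with candesartan is associated with lower CIMT, arterial stiffness, and inflammatory and endothelial function markers at 12 months".

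The baseline data will exist. Section 7.2.3 says "Blood samples will also be collected for APOE, inflammatory and endothelial markers", section 6.5 says "We will perform baseline, 12 months assessments of the inflammatory biomarkers", and Table 2 schedules vascular imaging, brain MRI and neuropsychological testing at baseline and 12 months.

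**The concern.** Randomization makes the arms comparable, so the treatment effect on a marker is estimated without confounding. It does not randomize marker levels within an arm. People with stiffer arteries at 12 months mostly had stiffer arteries at entry, and they may already have had worse perfusion or cognition. The background takes such a link as given: "Increased vascular stiffness and atherosclerosis reflected by higher carotid intima-media thickness (CIMT) contributes to vascular brain injury and cognitive impairment". With no baseline terms, γ absorbs it.

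Aim 3 asks whether changes in these markers explain candesartan's effect. Under the planned models, a real drug effect on a marker plus an old cross-sectional correlation can be enough to reject the mediation null, even when changing the marker does nothing to the brain outcome. Depending on the sign of the old correlation, the same flaw can also hide real mediation.

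**Working it through.** **What β1 − β2 estimates.** Write mediator = δ + a × treatment + error and substitute it into the second regression. The total treatment coefficient is β2 + aγ, so β1 − β2 = aγ. Here a is the treatment shift in the marker and γ is the marker-outcome slope within arms. If a = 0 the product centres on zero, whatever γ contains.

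**Inputs from the documents.** The final sample is 140, allocated 1:1 (sections 10.2 and 10.6). Section 10.6 also says "The 1 year correlation with baseline repeated measures ranged from 0.3 to 0.5 in our pilot data". The documents give no power, effect size or error rate for mediation, so there is no planned figure to reproduce.

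**Assumptions.** True mediation is zero and 12-month levels are analysed. The baseline marker-outcome correlation ρ is 0.3. The marker shift is 0, 0.24 or 0.48 SD; the two non-zero values are borrowed from the CO2-reactivity and TMT-B outcome effects in section 10.6. Intervals are 95% percentile bootstrap.

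**Expected spurious effect (SD of outcome).**
- Stable trait behind both measures at both visits: γ = ρ. This gives 0.24 × 0.3 = 0.072 and 0.48 × 0.3 = 0.144.
- Association carried only through the measured baselines: γ = ρ × the two one-year correlations. This gives 0.24 × 0.3 × 0.3 × 0.3 = 0.006 at the low end, 0.48 × 0.3 × 0.5 × 0.5 = 0.036 in the middle and 0.48 × 0.3 × 0.9 × 0.9 = 0.117 at the high end.

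**Simulated false mediation findings.** Each setting used 1000 trials of 500 resamples; 0.5/0.5 at 0.48 SD was rerun with 3000 × 1000. The Monte Carlo standard error for 1000 trials is √(0.05 × 0.95/1000) = 0.7 points near 5% and √(0.5 × 0.5/1000) = 1.6 points near 50%. Adjusted means that baseline mediator and baseline outcome are in both models.

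| One-year correlations of the two measures | Measured baselines, 0.24 SD: planned → adjusted | Measured baselines, 0.48 SD: planned → adjusted | Stable trait, adjusted: 0.24 SD | Stable trait, adjusted: 0.48 SD |
|---|---|---|---|---|
| 0.3/0.3 | 1.5% → 0.8% | 5.1% → 5.3% | 17.0% | 50.9% |
| 0.5/0.5 | 3.0% → 2.0% | 12.2% → 5.6% | 9.1% | 24.5% |
| 0.7/0.5 | 6.5% → 2.4% | 19.2% → 6.3% | 7.8% | 15.4% |
| 0.8/0.7 | 11.8% → 2.8% | 41.6% → 4.9% | 5.6% | 8.7% |
| 0.9/0.9 | 25.4% → 4.5% | 65.7% → 5.9% | 5.0% | 5.7% |

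In the stable-trait model the planned analysis gave 27.3-29.9% at 0.24 SD and 74.7-78.3% at 0.48 SD. With no shift, the planned analysis gave 0.2-6.4%.

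**Weaker correlation.** With ρ of 0.1-0.2 and a shift of 0.48 SD, the planned analysis gave 4.4-20.1% (measured baselines) and 18.6-51.3% (stable trait).

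**Separate runs.** A second program (600 trials of 1000 resamples, ρ of 0.2 or 0.3) gave, for the planned analysis, 17-30% at 0.24 SD and 51-83% at 0.5 SD under a stable trait. With measured baselines it gave 1-11% at correlations of 0.3-0.5 and 13-70% at 0.9. With no shift, false findings stayed at or below about 5%.

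**When mediation is real.** Assume 0.3 SD of outcome per SD of mediator change and a shift of 0.48 SD, so the true effect is 0.3 × 0.48 = 0.144. With ρ from 0 to 0.3, power was 0.63-0.78 as planned against 0.86 adjusted at 0.5/0.5, and 0.22-0.75 against 0.85 at 0.8/0.7. Mean estimates were 0.055-0.148 as planned and 0.145 adjusted.

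**The case against.** The best counter-argument is that the plan may intend change scores. Section 10.1 speaks of improvements in the markers going with improved imaging and less cognitive decline, and the part (a) cognitive test is treatment by visit. On change scores, false findings were 1-6% in the stable-trait model and at most 13% in the other. This stands as a reason to state the time point. It does not settle the matter, because Hypotheses 3 name marker levels at 12 months and part (a) names 12-month dependent variables.

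The equations may also be shorthand, with Table 3 supplying the covariates. Even then the baseline mediator would be missing.

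The size rests on undocumented inputs. At the pilot's correlations with baseline-only linkage the excess is small, and at 0.3/0.3 with 0.48 SD adjustment makes no difference (5.1% against 5.3%). That is correct, but the correlations in section 10.6 are not given for any mediator, and section 6.3 reports EXAMINER test-retest reliability above 0.9. Higher stability cannot be ruled out.

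Fewer than 140 people will have imaging, because section 4.2 admits people who cannot be scanned. At an assumed 100-120, the stable-trait rate at 0.48 SD falls from about 78% to 55-70%, which is still material.

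The background's claim is causal, so part of γ may be the effect under study; the planned models cannot separate that part from the rest. The EXAMINER score's allowance for age, education and race may remove some shared causes for the cognitive outcome, but it does not help the imaging outcomes.

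Finally, baseline adjustment does not fully cure the problem when baselines are noisy. That also stands, and the fix allows for it.

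**Conclusion.** The concern holds, conditional on a treatment effect on the marker. Without one there is no excess false mediation. With one, the planned models can report a spurious effect of about 0.01-0.12 SD if the association runs through measured baselines, or 0.07-0.15 SD under a stable trait. False-positive rates range from negligible to about 78%. They depend on an assumed correlation of 0.3, assumed shifts of 0.24 and 0.48 SD, 12-month levels and 140 participants. The mechanism is algebraic and certain; its size in this trial is not known. Only Aim 3 is affected. The plan should be changed, but the primary comparison is not at risk.

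**What to change.** In section 10.5(b), state that 12-month mediator and outcome values are analysed. Add the baseline mediator, baseline outcome, randomization strata, prior stroke and prior ACEI/ARB use to **both** regressions. Fit both to the same participants and bootstrap β1 − β2 from those models. The simulations support the two baseline terms. The other covariates were not tested separately; they are included for consistency with part (a) and Table 3.

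State that adjustment reduces the bias but may not remove it when baselines are noisy, and that no other mediator-outcome confounding is assumed. Add two sensitivity analyses:
1. The residual mediator-outcome correlation that would bring each estimate to zero.
2. The same models on change scores. These suit a check rather than the main analysis, because they reached 13% false findings in one model.

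The cost is plan wording and a few model terms, with no new data collection. Participants without a baseline mediator or baseline outcome drop out of that model. The simulations showed no loss of power, though they reported no missing baselines.
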